18.0 Records and Data Collection Procedures

18.1 Submission Timetable

Data submission instructions for this study can be found in the Data Submission Schedule.

18.2 Event monitoring

See [Section 4.0](#) and Data Submission Schedule for the event monitoring schedule.

18.3 CRF completion

This study will use Medidata Rave for remote data capture (rdc) of all study data.

18.4 Site responsibilities

Each site will be responsible for insuring that all materials contain the patient's initials, MCCC registration number, and MCCC protocol number. Patient's name must be removed.

18.5 Supporting documentation

This study requires supporting documentation for diagnosis and progression prior to study entry as well as for evidence of response to study therapy and progression after study therapy.

Supporting documentation for diagnosis will include a pathology report from the most recent tumor tissue biopsy, most recent bone marrow biopsy report, and baseline imaging report. These reports should be uploaded into the Supporting Documentation: Baseline form in the Medidata Rave system ≤ 14 days after registration.

For response to treatment, supporting documentation includes an imaging report and, if applicable, a Bone Marrow Biopsy report..

For patients who progress after study therapy, supporting documentation may include an imaging report, bone marrow biopsy report, or pathology report.

18.6 Labelling of materials

Each site will be responsible for insuring that all materials contain the patient's initials, MCCC registration number, and MCCC protocol number. Patient's name must be removed.

18.7 Incomplete materials

Any materials deemed incomplete by the MCCC Operations Office will be considered "not received" and will not be edited or otherwise processed until the missing information is received. A list of the missing documents will be made available to the appropriate co-sponsor/participant.

18.8 Overdue lists

A list of overdue materials and forms for study patients will be generated monthly. The listings will be sorted by location and will include the patient study registration number. The appropriate co-sponsor/participant will be responsible to obtain the overdue material.

19.0 Budget

19.1 Costs charged to patient

All routine clinical care. The participant will be billed for pharmacy and administration charges and other ancillary expenses such as any oral medications prescribed at the time of discharge.

19.2 Tests to be research funded

Correlative studies described in Sections 14.0 and 17.0.

19.3 Other budget concerns

Nivolumab will be supplied by Bristol-Myers Squibb.

Protocol administration, study coordinator time, data management, and statistical analysis efforts will be funded by a grant from Bristol-Myers Squibb.

T-Cell Leukemia Lymphoma Foundation will provide funding for investigator effort.

Appendix I ECOG Performance Status

ECOG PERFORMANCE STATUS*	
Grade	ECOG
0	Fully active, able to carry on all pre-disease performance without restriction
1	Restricted in physically strenuous activity but ambulatory and able to carry out work of a light or sedentary nature, e.g., light house work, office work
2	Ambulatory and capable of all selfcare but unable to carry out any work activities. Up and about more than 50% of waking hours
3	Capable of only limited selfcare, confined to bed or chair more than 50% of waking hours.
4	Completely disabled. Cannot carry on any selfcare. Totally confined to bed or chair.
5	Dead

*As published in Am. J. Clin. Oncol.:

The ECOG Performance Status is in the public domain therefore available for public use. To duplicate the scale, please cite the reference above and credit the Eastern Cooperative Oncology Group, Robert Comis M.D., Group Chair.

[figure not shown]
From http://www.ecog.org/general/perf_stat.html

Appendix II Adverse Event Management Algorithms

(excerpted from Nivolumab Investigator Brochure version 15, June 2016)

Hepatic Adverse Event Management Algorithm

Rule out non-inflammatory causes. If non-inflammatory cause, treat accordingly and continue I-O therapy. Consider imaging for obstruction.

[figure not shown]

Patients on IV steroids may be switched to an equivalent dose of oral corticosteroids (e.g. prednisone) at start of tapering or earlier, once sustained clinical improvement is observed. Lower bioavailability of oral corticosteroids should be taken into account when switching to the equivalent dose of oral corticosteroids.

*I-O therapy may be delayed rather than discontinued if AST/ALT ≤ 8 x ULN and T.bili ≤ 5 x ULN. **The recommended starting dose for grade 4 hepatitis is 2 mg/kg/day methylprednisolone IV.

Skin Adverse Event Management Algorithm

Rule out non-inflammatory causes. If non-inflammatory cause, treat accordingly and continue I-O therapy.

[figure not shown]

Patients on IV steroids may be switched to an equivalent dose of oral corticosteroids (e.g. prednisone) at start of tapering or earlier, once sustained clinical improvement is observed. Lower bioavailability of oral corticosteroids should be taken into account when switching to the equivalent dose of oral corticosteroids.

*Refer to NCI CTCAE v4 for term-specific grading criteria.

Neurological Adverse Event Management Algorithm

[figure not shown]
Rule out non-inflammatory causes. If non-inflammatory cause, treat accordingly and continue I-O therapy.

Patients on IV steroids may be switched to an equivalent dose of oral corticosteroids (e.g. prednisone) at start of tapering or earlier, once sustained clinical improvement is observed. Lower bioavailability of oral corticosteroids should be taken into account when switching to the equivalent dose of oral corticosteroids.

Pulmonary Adverse Event Management Algorithm

[figure not shown]
Rule out non-inflammatory causes. If non-inflammatory cause, treat accordingly and continue I-O therapy. Evaluate with imaging and pulmonary consultation.

Patients on IV steroids may be switched to an equivalent dose of oral corticosteroids (e.g. prednisone) at start of tapering or earlier, once sustained clinical improvement is observed. Lower bioavailability of oral corticosteroids should be taken into account when switching to the equivalent dose of oral corticosteroids.

GI Adverse Event Management Algorithm

[figure not shown]
Rule out non-inflammatory causes. If non-inflammatory cause is identified, treat accordingly and continue I-O therapy. Opiates/narcotics may mask symptoms of perforation. Infliximab should not be used in cases of perforation or sepsis.

Patients on IV steroids may be switched to an equivalent dose of oral corticosteroids (e.g. prednisone) at start of tapering or earlier, once sustained clinical improvement is observed. Lower bioavailability of oral corticosteroids should be taken into account when switching to the equivalent dose of oral corticosteroids.

Endocrinopathy Adverse Event Management Algorithm

[figure not shown]
Rule out non-inflammatory causes. If non-inflammatory cause is identified, treat accordingly and continue I-O therapy. Consider visual field testing, endocrinology consultation, and imaging.

Patients on IV steroids may be switched to an equivalent dose of oral corticosteroids (e.g. prednisone) at start of tapering or earlier, once sustained clinical improvement is observed. Lower bioavailability of oral corticosteroids should be taken into account when switching to the equivalent dose of oral corticosteroids.

Renal Adverse Event Management Algorithm

Rule out non-inflammatory causes. If non-inflammatory cause is identified, treat accordingly and continue I-O therapy.

Patients on IV steroids may be switched to an equivalent dose of oral corticosteroids (e.g. prednisone) at start of tapering or earlier, once sustained clinical improvement is observed. Lower bioavailability of oral corticosteroids should be taken into account when switching to the equivalent dose of oral corticosteroids.

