8.2 Dose Delay Criteria for Nivolumab

See Management Algorithms ([Appendix II](#))

→ → Use the NCI Common Terminology Criteria for Adverse Events (CTCAE) version 4.0* unless otherwise specified ← ←

CTCAE System/Organ/Class (SOC)	Event	Agent	Action
Investigations	Alanine aminotransferase increased, Aspartate aminotransferase increased, and/or Blood bilirubin increased	Nivolumab	
If a patient has a baseline AST/ALT that is within the normal limits, delay dosing for nivolumab-related \geqGrade 2 (>3-5 x ULN) elevations and start corticosteroids at 0.5 to 1 mg/kg/day prednisone equivalents. Nivolumab may be resumed if the value improves to Grade 1 (≤ 3 x ULN) or better.
 
If a patient has a baseline AST/ALT in the Grade 1 range (ULN to ≤ 3 x ULN), delay dosing for nivolumab-related \geqGrade 3 (>5 to 8 x ULN) elevations and start corticosteroids at 1 to 2 mg/kg/day prednisone equivalents. Nivolumab may be resumed if the value improves to Grade 2 (>3 to 5 x ULN) or better.
 
If a patient has a baseline total bilirubin that is within normal limits, delay dosing for nivolumab-related Grade 2 elevations (>1.5-3 x ULN) and start corticosteroids at 0.5 to 1 mg/kg/day prednisone equivalents. Nivolumab may be resumed if the bilirubin improves to Grade 1 (≤ 1.5 x ULN) or better.
 
If a patient has a baseline total bilirubin that is in the Grade 1 range (ULN to ≤ 1.5 x ULN), delay dosing for nivolumab-related Grade 3 elevations (>3-5 x ULN) and start corticosteroids at 1 to 2 mg/kg/day prednisone equivalents.

CTCAE System/Organ/Class (SOC)	Event	Agent	Action
			
Nivolumab may be resumed if the total bilirubin improves to Grade 2 ($\leq 3 \times$ ULN) or better.
 
Doses of nivolumab should be discontinued permanently for the following LFT abnormalities: AST or ALT $>8 \times$ ULN (Grade 3) or drug-induced liver injury (DILI); Total bilirubin $>5 \times$ ULN (Grade 3) or DIL; concurrent AST or ALT $>3 \times$ ULN and total bilirubin $>2 \times$ ULN. Administer corticosteroids 1 to 2 mg/kg/day prednisone equivalents.
 
Subjects with combined Grade 2 AST/ALT meeting discontinuation parameters: go to event monitoring per Section 4.2.

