8.3 Discontinuation Criteria for Nivolumab

Treatment should be permanently discontinued for the following:

- Any Grade 2 drug-related uveitis or eye pain or blurred vision that does not respond to topical therapy and does not improve to Grade 1 severity within the re-treatment period OR requires systemic treatment
- Any Grade 3 non-skin, drug-related adverse event lasting >7 days, with the following exceptions for drug-related laboratory abnormalities, uveitis, pneumonitis, bronchospasm, hypersensitivity reactions, and infusion reactions, and endocrinopathies:
 - Grade 3 drug-related uveitis, pneumonitis, bronchospasm, hypersensitivity reaction, or infusion reaction of any duration requires discontinuation
 - Grade 3 drug-related endocrinopathies adequately controlled with only physiologic hormone replacement do not require discontinuation
 - Grade 3 drug-related laboratory abnormalities do not require treatment discontinuation except those noted below

- Grade 3 drug-related thrombocytopenia >7 days or associated with bleeding requires discontinuation
- Any drug-related liver function test (LFT) abnormality that meets the following criteria require discontinuation:
 - AST or ALT >8 x ULN
 - Total bilirubin >5 x ULN
 - Concurrent AST or ALT >3 x ULN and total bilirubin >2 x ULN
- Any Grade 4 drug-related adverse event or laboratory abnormality, except for the following events which do not require discontinuation:
 - Isolated Grade 4 amylase or lipase abnormalities that are not associated with symptoms or clinical manifestations of pancreatitis and decrease to < Grade 4 within 1 week of onset.
 - Isolated Grade 4 electrolyte imbalances/abnormalities that are not associated with clinical sequelae and are corrected with supplementation/appropriate management within 72 hours of their onset
 - Grade 4 lymphopenia or leucopenia
 - Grade 4 drug-related endocrinopathy adverse events, such as adrenal insufficiency, ACTH deficiency, hyper- or hypothyroidism, or glucose intolerance, which resolve or are adequately controlled with physiologic hormone replacement (corticosteroids, thyroid hormones) or glucose-controlling agents, respectively, may not require discontinuation after discussion with and approval from the Investigator [as allowed by protocol]
- Any dosing interruption lasting >6 weeks with the following exceptions:

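### The Appendix II hepatic footnote allows delay at AST/ALT up to 8 and bilirubin up to 5 × ULN without excepting the combined-elevation stop in Sections 8.2 and 8.3

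*Combined protocol and SAP*

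**What the plan says.** Section 8.3 is the list of reasons to stop nivolumab for good. On the liver it says: "Any drug-related liver function test (LFT) abnormality that meets the following criteria require discontinuation". Three criteria follow: AST or ALT above 8 × ULN, total bilirubin above 5 × ULN, and "Concurrent AST or ALT >3 x ULN and total bilirubin >2 x ULN". Other Grade 3 laboratory findings are treated leniently: "Grade 3 drug-related laboratory abnormalities do not require treatment discontinuation except those noted below".

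The liver entry of the Section 8.2 table repeats the three numeric criteria under "Doses of nivolumab should be discontinued permanently for the following LFT abnormalities". It also names DILI as a reason to stop ("ULN (Grade 3) or drug-induced liver injury (DILI); Total bilirubin") and sends patients with combined Grade 2 elevations that meet the discontinuation parameters to event monitoring.

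Section 8.2 opens with a pointer to Appendix II ("See Management Algorithms"), and Section 9.6 sends the reader there again for further algorithms taken from the investigator's brochure. The asterisked note under the hepatic algorithm reads: "I-O therapy may be delayed rather than discontinued if AST/ALT ≤ 8 x ULN and T.bili ≤ 5 x ULN".

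Section 8.0 makes the modifications in its table strict for the first two cycles and guidance after that. No section ranks Appendix II against Section 8.

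**The concern.** The footnote's two limits are the exact complements of the first two numeric stop criteria. The third criterion, the combined elevation, has no counterpart in it. A clinician who goes to Appendix II, as Section 8.2 directs, could read the footnote as permission to hold the drug and keep open re-treatment of a patient whom the protocol twice says must stop.

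The combination is the clinically important one. Its numeric limits are those of potential DILI in Section 10.85, and Section 8.2 shows that it is meant to act well below the footnote's limits, at combined Grade 2.

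What is at stake is the safety of an individual patient. The response endpoint, sample size, error rates and analyses do not depend on it.

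**Working it through.** No figure in the plan needs reproducing; this is a comparison of threshold rules. Let A be AST or ALT and B total bilirubin, both in multiples of ULN, with the abnormality judged drug-related.

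**Rules**
- Numeric stop (8.2 and 8.3): A > 8, or B > 5, or (A > 3 and B > 2).
- Non-numeric stop (8.2): DILI.
- Delay permitted (Appendix II footnote): A ≤ 8 and B ≤ 5.

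| Values | 8.2 and 8.3, numeric | Footnote |
|---|---|---|
| A > 8 | stop | delay not offered |
| B > 5 | stop | delay not offered |
| 3 < A ≤ 8 and 2 < B ≤ 5 | stop (combined rule) | delay permitted |
| A ≤ 8 and B ≤ 5, with A ≤ 3 or B ≤ 2 | no numeric stop | delay permitted |

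Only the third row conflicts. The overlap of the footnote with the two single-value stops is empty.

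**Example: A = 6, B = 4.** The footnote's conditions hold (6 ≤ 8 and 4 ≤ 5). The single-value stops are not met (6 is not above 8; 4 is not above 5). The combined stop is met (6 > 3 and 4 > 2), and it is the only purely numeric liver-test stop that is. DILI may apply as well: Section 10.85 uses the same two limits, and adds no initial cholestasis and no other immediately apparent cause.

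**How far the zone could shrink.** The footnote qualifies whichever flowchart box carries the asterisk, and that box is not visible. Using Section 8.2's ranges (Grade 2: A above 3 to 5, B above 1.5 to 3; Grade 3 starts at A above 5, B above 3):
- No grade restriction: 3 < A ≤ 8 and 2 < B ≤ 5. This is the upper bound.
- Assume the box needs Grade 3 in either value: the corner 3 < A ≤ 5 with 2 < B ≤ 3 drops out. ALT 4 with bilirubin 2.5 would then no longer be a conflict.
- Assume it needs Grade 3 in both: 5 < A ≤ 8 and 3 < B ≤ 5 remains.
- Assume it covers Grade 4 only: nothing remains. Section 8.2 still labels A > 8 and B > 5 as Grade 3, so on those labels the footnote could never apply.

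The example A = 6, B = 4 lies in the first three zones.

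**Which text applies in later cycles.** The relaxation after two cycles in Section 8.0 refers to its table. Section 8.3 is a separate list with no cycle limit, so its combined rule stays mandatory throughout.

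**Frequency.** The documents give no rate for the concurrent event. Section 15.17 lists increased bilirubin at 0.1% to below 1%. Assuming that range carries over to the 39 patients planned in Section 16.22, the expected number with any such increase is 39 × 0.001 = 0.039 to below 39 × 0.01 = 0.39. The concurrent event should be rarer still.

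**The case against.** The strongest objection is that the footnote cannot be judged apart from its flowchart. The chart may itself handle combined elevation, and its absence from the supplied text is not a fault of the plan. This stands as a limit on size and confidence. It does not remove the point, because the footnote's own sentence is visible and contains no exception.

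Second, the footnote only permits and Section 8.3 requires. Stopping the drug satisfies every text, and a generic brochure excerpt should yield to the protocol's own nivolumab criteria. This also stands: Section 8.3 is the better-supported controlling rule. What is missing is a sentence saying so, when two sections send clinicians to the appendix.

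A reader might go further in three ways that the documents do not support:
- *That the combined rule is the only liver stop protecting a patient such as ALT 6 with bilirubin 4 × ULN.* Section 8.2 also stops for DILI, and Section 8.3 lets the investigator stop for substantial clinical risk.
- *That Section 8.2 itself allows re-dosing.* Its rule for patients whose baseline AST/ALT is already in the Grade 1 range says "Nivolumab may be resumed if the value improves to Grade 2", and the bilirubin rule is similar. Those lines concern single values. The same entry goes on to require a permanent stop for the combination and sends combined Grade 2 cases to event monitoring, so read whole it does not allow resumption.
- *That the combined stop becomes optional after cycle 2.* That relaxation does not reach Section 8.3.

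**Conclusion.** The inconsistency is real and minor. The visible footnote offers delay in a range where Sections 8.2 and 8.3 require permanent discontinuation: at most AST/ALT above 3 and up to 8 × ULN together with bilirubin above 2 and up to 5 × ULN. The range may be smaller, depending on the box that the asterisk marks. Confidence is low to medium for that reason.

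The practical consequence is limited. The mandatory rule is stated twice, DILI is a separate reason to stop, and events meeting Section 10.85 must be reported as serious adverse events. The event is expected to be rare, although that rests on the general bilirubin frequency in Section 15.17 and not on a rate for this population. No estimate, decision rule or error rate changes.

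**What to change.** Extend the Appendix II hepatic footnote with an exception: AST or ALT above 3 × ULN together with total bilirubin above 2 × ULN, or DILI, requires permanent discontinuation under Sections 8.2 and 8.3. Add one sentence to Section 8.2 stating that the permanent-discontinuation criteria in 8.2 and 8.3 prevail over Appendix II in every cycle.

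The cost is one clause and one sentence, with no extra visits, tests or patients. If the flowchart already carries the combined rule, the edit only makes the footnote agree with it.

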Appendix III Specimen Checklist and Shipping Instructions

Blood Collection Kit Predolin Biobank

MC1681: Phase 2 Single-Arm, Open-Label Study of Nivolumab in Patients with Relapsed or Refractory Peripheral T-cell Lymphoma (PTCL)

**** PLEASE AVOID DRAWING OR SENDING SPECIMENS ON FRIDAYS AND HOLIDAYS****

Kit Contents:

- Small Styrofoam box and cardboard mailing sleeve
- Patient Information Form
- FedEx Airbill with pre-printed return address
- One 6ml ACD (yellow) collection tube
- One 10ml EDTA (purple) collection tube
- One 10ml Red Top collection tube
- Absorbent tube holder
- Zip lock specimen bag

Packing and Shipping Instructions:

1. Collect the following specimens:
 - Bone marrow – 6ml in one (1) ACD tube (Collected at Baseline only)

 - Peripheral blood – Draw:
 - 10ml in one (4) EDTA tube
 - 10ml in one (1) Red top tube

2. All specimens are to be clearly labeled with the protocol number MC1681, the patient's initials (last, first, middle), study patient ID (if available), type of sample (bone marrow or peripheral blood), and date of collection.
3. Place the tubes in the absorbent holder and seal in the zip lock specimen bag.
4. Place the filled specimen bag in the Styrofoam container.
5. Loosely pack with paper toweling.
6. Place the Styrofoam container and the Patient Information form within the cardboard mailing sleeve.
7. Prepare the package for shipping, applying packing tape as needed. Adhere the Fed Ex Airbill to the exterior of the box. Ship specimens via priority overnight delivery (next day delivery by 10am) the same day collected.
8. Notify Federal Express for pick-up and/or leave package at the designated FedEx drop-off location.

Please email [REDACTED] or call [REDACTED] to notify the laboratory when samples are being shipped. Indicate the protocol number MC1681, the Fed Ex tracking number, name and phone number of the contact person. The samples in prepared kits should be shipped to the following:

Predolin Biobank Attn: [REDACTED]
[REDACTED]
Rochester, MN [REDACTED]
